6.2.2. Handling of Missing Data

Missing data other than protocol-planned baseline values will be classified as missing completely at random (MCAR) or missing at random (MAR). MCAR can be confirmed by partitioning the data into two parts: one set containing the missing values, and the other containing the non-missing values. After partitioning the data, the t-test of mean difference is carried out in order to check whether there exists any difference in the sample between the two data sets. If the number of missing values is small, i.e. if the number of the cases is less than 5% of the sample, then the researcher can drop them. Otherwise, when analyzing using ITT population, model based multiple imputation (MI) will be used for both primary and secondary outcomes. The number of imputations will be the largest value of:

- 10, or
- The proportion of missing values for the actual variable * 100.

200 burn in iterations will be used for all analyses. Trace plots and distribution plots will be created to check the accuracy of imputations.

6.3. Analysis Supporting Secondary Objectives

Analysis of secondary end-points is not dependent on the analysis of the primary end-point.

Secondary Endpoint 1, Hypothesis 2. Treatment with VR-AD-1005 improves hydration control in patients with diarrhea due to *V. cholerae* infection. Null hypothesis is stated as no statistically

significant difference in the number of unscheduled hydration episodes as compared to placebo; alternative hypothesis 2 is stated as statistically significant improvement in hydration control, expressed as number of unscheduled rehydration episodes over the treatment period; in patients treated with VR-AD-1005. Unscheduled IV rehydration is defined as “receipt of IV fluid during the maintenance phase of hydration due to development of severe dehydration or some dehydration with high purging (>15 ml/kg/hour) or persistent vomiting (>3 episodes/hour), or failure to take ORS for any reason”

Secondary Endpoint 2, Hypothesis 3. Treatment with VR-AD-1005 shortens duration of diarrhea in patients with diarrhea due to *V. cholerae* infection. Null hypothesis is stated as no statistically significant difference in the duration of diarrhea as compared to placebo; alternative hypothesis 2 is stated as statistically significant reduction in the duration of diarrhea, expressed as number of days till normalization of stool, in patients treated with VR-AD-1005.

Secondary Endpoint 3, Hypothesis 4. Treatment with VR-AD-1005 shortens duration of stool output in excess of 200ml/hour in patients with diarrhea due to *V. cholerae* infection. Null hypothesis is stated as no statistically significant difference in the duration of stool output >200 ml/hour as compared to placebo; alternative hypothesis 2 is stated as statistically significant reduction in the duration of diarrheal output >200 ml/hour, expressed in hours, in patients treated with VR-AD-1005.

Analysis:

Secondary Endpoint 1, assessment of hydration control. There are two measurable parameters to be assessed in the patient hydration. Parameter 1 is the number of unscheduled hydration episodes. The numbers will be derived from the individual rehydration records, and the number of patients receiving IV rehydration will be expressed in % and compared for control and study intervention group. Alternatively, total number of IV rehydration episodes can be expressed as means for control and study intervention group and analyzed using Student's t-test. Parameter 2 is the volume of the oral rehydration solution received during the course of interventional treatment. Total volume of rehydration solution (oral and IV where applicable) will be derived from the individual rehydration records, expressed in ml/kg of patient weight, and analyzed as means using unpaired Student's t-test. Analysis subgroups will include 1) total hydration received over the course of study after first administration of interventional medication, and 2) hydration received during first 12 hours and 3) hydration received during first 24 hours.

Secondary Endpoint 2. Assessment of duration of diarrhea. Total duration of diarrheal illness is an important parameter in the assessment of antidiarrheal treatment efficacy. Study intervention is expected to reduce the overall duration of the diarrhea. Duration of diarrhea is assessed from first administration of study intervention until the termination of diarrhea, which is defined as first formed stool, or no stool for 12 consecutive hours. Duration of diarrhea will be derived from individual stool charts. Kaplan-Meier survival curves will be built to compare duration of diarrhea between control and intervention groups.

Secondary Endpoint 3. Duration of stool output in excess of 200ml/hour. As stated above, duration of diarrheal disease in cholera is limited, averaging 30-35 hours²⁴. This could mask the beneficial effect of antidiarrheal treatment (as measured solely by stool quantification) if high initial stool output terminates abruptly. In order to establish the time course of the study intervention's effect, in addition to analyzing the total duration of diarrhea in patients we need to introduce a parameter that combines the measured quantity of stool output and the time factor, addressing the question whether interventional medication can reduce the severity of diarrhea in the early stage of administration of study intervention. For analysis, individual stool charts will be used to calculate stool output per patient per 12-hour period and express it as stool volume in ml/hour. Duration of time when stool

output is in excess of 200ml/hour will be calculated for each participant, expressed as means for control and study intervention group and analyzed using Student's t-test.

Normal distribution is assumed for Endpoints 1 and 3. Non-parametric statistics is used in the analysis of Endpoint 2. Analysis will be conducted in the ITT, MITT and PP groups. Missing data and outliers will be handled using imputation technique. Non-adherence and lost to follow-up patients will be categorized into the appropriate group and handled accordingly. No subtractions will be made from the ITT group after randomization assignment.

6.4. Safety Analyses

Safety analysis is not the primary or secondary objective of this study, thus safety will be analyzed as summary statistics during treatment. AEs will be coded per Medical Dictionary for Regulatory Activities (MedDRA), and calculated. Each AE will be counted once only for a given participant, and presented using standard available criteria for severity, frequency, and relationship of AEs to study intervention. Start date, stop date, severity, relationship, expectedness, outcome, and duration will be reported for each SAE. Adverse events leading to premature discontinuation from the study intervention and serious treatment-emergent AEs will be listed. Proportion of the patients presented with AE or SAE will be calculated for IP and Placebo arms as a fraction of the total number of participants per arm and expressed as percent. Percentage of AE and SAE occurrence will be compared between IP and placebo groups to provide information regarding the safety of the investigational product.

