- After discharge, participants will be followed up with weekly phone calls to check on their health and wellbeing and also ascertain, if they are experiencing any side effects of the treatment. For participants without phone, the phone number of their guardian or neighbor will be taken for the follow up. Where participant cannot be reached via phone, their personal address will be followed to conduct the follow up. After three attempts of phone calls and one home visit, participants that cannot be reached will be declared lost to follow up.

[REDACTED]

[REDACTED]

[REDACTED]

[REDACTED]

[REDACTED]

[REDACTED]

[REDACTED]

[REDACTED]

[REDACTED]

[REDACTED]

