4.7. Adverse Events and Serious Adverse Events

4.7.1. Definitions of AE, SAE and ADR

Terminology according to ICH S2A:

Adverse event: An adverse event (AE) can therefore be any unfavourable and unintended sign (including an abnormal laboratory finding, for example), symptom, or disease temporally associated with the use of a medicinal product, whether or not considered related to the medicinal product.

Adverse Drug Reaction (ADR): In the *pre-approval clinical experience* with a new medicinal product or its new usages, particularly as the therapeutic dose(s) may not be established:

Unexpected Adverse Drug Reaction: An adverse reaction, the nature or severity of which is not consistent with the applicable product information (e.g., Investigator's Brochure for an unapproved investigational medicinal product).

Serious Adverse Event or Adverse Drug Reaction: During clinical investigations, adverse events may occur which, if suspected to be medicinal product-related (adverse drug reactions), might be significant enough to lead to important changes in the way the medicinal product is developed (e.g.,

change in dose, population, needed monitoring, consent forms). This is particularly true for reactions which, in their most severe forms, threaten life or function. Such reactions should be reported promptly to regulators.

Serious adverse event (experience) or reaction is any untoward medical occurrence that at any dose:

** results in death,*

** is life-threatening,*

NOTE: The term "life-threatening" in the definition of "serious" refers to an event in which the patient was at risk of death at the time of the event; it does not refer to an event which hypothetically might have caused death if it were more severe.

** Requires inpatient hospitalisation or prolongation of existing hospitalisation,*

** results in persistent or significant disability/incapacity, or*

** is a congenital anomaly/birth defect.*

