4.11. Discontinuation of Trial Intervention and Participant Withdrawal from Trial

Participants may withdraw from a research study for any reason, even without mentioning any reason. The participants will be able to receive standard treatment of the hospital without any penalty. For evaluation and reporting purposes, researchers may ask participants for their reasons for early withdrawal.

An investigator may discontinue trial intervention or withdraw a participant from the study for the following reasons:

- Significant study intervention non-compliance.
- If any adverse event (AE), Serious adverse events (SAE), laboratory abnormality, or other medical condition or situation occurs, continued participation in the study would not be in the best interest of the participant.
- Disease progression which requires discontinuation of the study intervention
- If the participant meets an exclusion criterion (either newly developed or not previously recognized) that precludes further study participation.
- Participant unable to receive study intervention for 3 days.
- Reporting over-dose
- protect a participant from excessive risk or risk with a demonstrated lack of benefits (e.g., a participant experiences serious side-effect without the anticipated therapeutic effects), or
- maintain the integrity of the data (e.g., a participant is not following study procedures or may be deliberately providing false information).

Whenever an investigator terminates a subject's participation in research, the investigator must explain to the participant the reasons for the termination and, as appropriate, other treatment options available to the participant.

The data to be collected at the time of study intervention discontinuation will include the following:

- Physical examination
- Vital signs
- Complete blood count (CBC)
- Blood Basic metabolic panel, including Serum electrolytes and creatinine
- Assessment of vomiting
- Assessment of stool output
- Assessment of dehydration
- Assessment of IV and oral ORS and oral water intake
- Assessment of urine output
- Administration of questionnaires or other instruments helping participants to register symptoms, such as stool charts.
- Assessment of adverse events.

Follow-up calls will be made with patients who completed the protocol with questionnaires focusing on the side effects. Calls will be made once a week during the 28-day follow-up period.

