4.12. Lost to Follow-up

A participant will be considered lost to follow-up if he or she fails to return for three out of four scheduled phone calls or one missed in-person visit (for withdrawals) and is unable to be contacted by the study site staff. The following actions must be taken if a participant fails to return to the clinic for a required study visit: The site will attempt to contact the participant and reschedule the missed visit within 7 days and counsel the participant on the importance of maintaining the assigned visit schedule and ascertain if the participant wishes to and/or should continue in the study.

Before a participant is deemed lost to follow-up, the investigator or designee will make every effort to regain contact with the participant (where possible, 3 telephone calls and/or electronic messages, one home visit). These contact attempts should be documented in the participant's medical record or study file.

Should the participant continue to be unreachable, he or she will be considered to have been lost to follow-up and will be excluded from the long-term safety data analysis.

Since follow-up occurs after the completion of the treatment course, loss to follow-up is not critical for the primary and secondary endpoints and treatment data obtained during the course of the trial will remain valid.

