
diarrhea following VR-AD-1005 administration.
 
 • Evaluation of safety and tolerability of VR-AD-1005 in addition to standard of care (SoC) versus SoC with placebo in adults with symptomatic cholera via documentation of adverse events, physical examination, and vital signs. 	
the treatment for both treatment groups.
 
 • Time until clinical recovery (defined as disappearance of watery stool and two consecutive passages of soft stool). Duration of diarrhea until the passage of first non-watery stool (soft/loose) or no stool for 12 hours or the end of treatment (72 hours) will be derived from date and time records in daily stool charts. • Number of subjects with clinical recovery as above within treatment group. The number of subjects with clinical recovery will be recorded as total for the entire treatment duration, and as number of recoveries per each 24-hour period of treatment. • Number of unscheduled IV rehydration episodes per treatment. The number of unscheduled IV rehydration episodes per treatment will be recorded for the entire duration of the treatment. Unscheduled IV rehydration is defined as "receipt of IV fluid during the maintenance phase of hydration due to development of severe dehydration or some dehydration with high purging (>15 ml/kg/hour) or persistent vomiting (>3 episodes/hour), or failure to take ORS for any reason" • Duration of IV rehydration for the entire treatment period per treatment group and per each 24- hour period of treatment. • Safety will be measured by the proportion of patients that will present with AE/SAE as defined in Appendix II following administration of VR-AD- 1005. 	
measure of hydration status of the participants, as well as providing a measure of the duration of the illness. Dehydration is the primary cause of death in cholera; duration of illness is the primary measure of the burden on the healthcare system and quality of life/productivity loss for cholera patients. Assessment of reduction in the need for unscheduled intravenous rehydration and time until switch to oral rehydration therapy will allow to assess the benefit of VR-AD-1005 for in-patient management of cholera cases. Thus, secondary end-points allow to characterize the benefits related to potential improvements in the clinical course of the disease, case management and quality of life for cholera patients.

---	--	--

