Appendix II : ADVERSE EVENTS AND SERIOUS ADVERSE EVENTS – DEFINITIONS, SEVERITY, AND CASUALTY

Definitions

Adverse event: An untoward medical occurrence after exposure to a medicine, which is not necessarily caused by that medicine.

Serious Adverse event: An adverse reaction that results in death, is life-threatening, requires hospitalisation or prolongation of existing hospitalisation, results in persistent or significant disability or incapacity, or is a birth defect

Assessment of severity

The terms "severe" and "serious" are not synonymous. Severity refers to the intensity of an adverse event (rated as mild, moderate, or severe, or according to a pre-defined grading criterion; the event itself may be of relatively minor medical significance (such as severe headache without any further findings).

Severity and seriousness need to be independently assessed for each adverse event recorded on the CRF.

Serious adverse events are required to be reported by the Investigator to the Sponsor immediately (i.e., no more than 24 hours after learning of the event).

The assessing adverse event severity table below will be used for assessing severity for adverse events.

Table -Adverse Event Severity Grading Scale

Grade	Severity
1	Mild; asymptomatic or mild symptoms; clinical or diagnostic observations only; or intervention not indicated
2	Moderate; minimal, local, or non-invasive intervention indicated; or limiting age-appropriate instrumental activities of daily living ^a
3	Severe or medically significant, but not immediately life-threatening; hospitalization or prolongation of hospitalization indicated; disabling; or limiting self-care activities of daily living ^b
4	Life-threatening consequences or urgent intervention indicated ^d
5	Death related to adverse event ^d

Note:

^a Instrumental activities of daily living refer to preparing meals, shopping for groceries or clothes, using the telephone, managing money, etc.

^b Examples of self-care activities of daily living include bathing, dressing and undressing, feeding oneself, using the toilet, and taking medications, as performed by patients who are not bedridden.

^c If an event is assessed as a "significant medical event," it must be reported as a serious adverse event

^d Grade 4 and 5 events must be reported as serious adverse events

Assessment of causality

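### The 28-day safety data have no planned analysis, and the plan contradicts itself on whether safety is an objective, who is followed and counted, and what an SAE is

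*Combined protocol and SAP*

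**What the plan says.** **Status and window.** Section 6.4: "Safety analysis is not the primary or secondary objective of this study, thus safety will be analyzed as summary statistics during treatment". Table 1 in section 5.0 lists among the secondary objectives: "Evaluation of safety and tolerability of VR-AD-1005 in addition to standard of care (SoC) versus SoC with placebo".

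**Follow-up.** Section 4.11: "Follow-up calls will be made with patients who completed the protocol with questionnaires focusing on the side effects", and then "Calls will be made once a week during the 28-day follow-up period". Section 4.3 sets no completion condition; after discharge, "participants will be followed up with weekly phone calls to check on their health and wellbeing". Section 4.9 likewise describes calls or home visits for participants generally. Section 4.12 mentions an in-person visit for withdrawals that is scheduled nowhere else. In the Appendix I schedule the adverse-event row stops at end of treatment, and there is no follow-up column.

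**Lost patients.** Section 4.12 says that they "will be excluded from the long-term safety data analysis". It adds that data from the treatment period stay valid.

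**Who is counted.** Section 6.4 divides by all participants in each arm and lists AEs that led to stopping treatment. Section 4.4.6.1 assigns to a group, for analysis, only those who completed the trial. Section 4.3 stops treatment in patients whose culture is negative and leaves them out of the final analysis.

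**SAE definition.** Table 1 refers the safety endpoint to Appendix II, which reads "Serious Adverse event: An adverse reaction that results in death, is life-threatening". Section 4.7.1 reads "Serious adverse event (experience) or reaction is any untoward medical occurrence that at any dose".

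**The concern.** This is a phase II efficacy and safety trial of a new fixed-dose combination, with 75 patients per arm. Section 6.4 justifies its narrow window by a premise that Table 1 contradicts. As a result the trial would collect four weeks of follow-up without saying how to analyse it.

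The other passages affect the same result. A site that follows section 4.11 literally would not call a patient who stopped because of an adverse event. A patient who reports an event on one call and is later declared lost could drop out of the long-term summary. A dosed patient whose culture is negative was exposed to the product but may appear in no safety table. A serious event attributed to cholera and not to the product may or may not count as an SAE, depending on which definition the coder uses.

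At stake is whether the AE and SAE proportions describe everyone exposed over the whole period observed, and whether two analysts with this plan would produce the same table.

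**Working it through.** **Design figures.** The plan gives no rate, precision or power for safety. Its only computed design figures are the power for stool output, 0.82 at 50 per arm and 0.94 at 75 per arm. With a difference of 0.33 × 280 = 92.4 g/kg, SD 156 and a two-sided t-test at 5%, the noncentral t gives 0.835 and 0.950. They reproduce closely but do not bear on safety.

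**Window without analysis.** Inputs: three treatment days (72 hours, Table 1) and 28 days of follow-up (section 4.11). The start of the 28 days is not stated.
- If they start at first dose: (28 − 3)/28 = 25/28 = 89.3%.
- If they start after treatment: 28/(28 + 3) = 28/31 = 90.3%.

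This is a share of calendar time, not of events.

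**Lost patients.** Section 4.12 allows a patient to be declared lost after missing three of four calls, so one call may have been answered. Exclusion from the long-term analysis would then remove that answered contact. Counting to last contact would keep it.

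**Who is counted.** Take a patient who received doses, had an adverse event and then either stopped or proved culture-negative. Under 6.4 the patient is in the denominator. Under 4.4.6.1 a non-completer is assigned to no group. Under 4.3 a culture-negative patient is out of the final analysis. No safety set is defined to settle this. At 75 per arm, one patient moves a proportion by 1/75 = 1.3 percentage points.

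**SAE definition.** Consider a hospital stay prolonged by an event judged unrelated and graded 3. Section 4.7.1 makes it an SAE. The Appendix II definition does not, because it requires a reaction. Appendix II narrows the gap itself: grade 4 and 5 events, and events called significant medical events, must be reported as SAEs with no condition on relatedness. What remains exposed is serious events below grade 4 that are judged unrelated and not called significant.

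**Illustration only.** Suppose the 28-day data were analysed but only completers were called. Let f be the share not followed and R their post-treatment event risk relative to those followed. Missed share = fR/[(1 − f) + fR]. Neither input is in the documents; both are assumptions.
- f = 0.05, R = 1: 0.05/1.00 = 5%
- f = 0.10, R = 2: 0.20/1.10 = 18%
- f = 0.20, R = 4: 0.80/1.60 = 50%

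A range this wide shows only that the size cannot be fixed in advance.

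**The case against.** Four stronger readings are tempting, and the documents do not support them.

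1. *The 6.4 analysis leaves out early stoppers.* It does not. Its denominator is all participants per arm, it lists AEs leading to discontinuation, and section 4.11 requires an AE assessment at discontinuation. The completer-only rule is in 4.4.6.1 and conflicts with 6.4.
2. *Early stoppers get no calls.* Section 4.11 implies this, but 4.3 and 4.9 describe calls to participants generally and 4.12 refers to a visit for withdrawals. This is a contradiction, not a settled exclusion.
3. *Data from lost patients are discarded.* Section 4.12 keeps the treatment-period data, and section 7.1 retains collected data in the database and reports safety events. The exclusion is limited to the long-term analysis.
4. *Unrelated serious events vanish, and the product is flattered.* Section 4.7.4 records all AEs whatever their relationship, Appendix II does not require an AE to be caused by the medicine, and 6.4 reports relationship for each SAE. Unrelated events therefore stay in the AE proportion. Assessment is blinded, and nothing in the documents points to loss that differs between arms.

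It is also fair to say that 6.4 still compares AE and SAE percentages by arm, so its denial that safety is an objective does not remove the comparison. Section 4.4.4 describes the product as not absorbed, and it is given for three days, so events may cluster early.

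These points limit the claim about bias. They do not supply an analysis of the follow-up data, a safety set or a single SAE definition.

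**Conclusion.** The point holds as a gap and a set of contradictions. As written, 25 of 28 or 28 of 31 days of safety observation (89-90%) have no planned analysis. This rests only on a three-day treatment period and the stated 28 days. The conflicts over who is called, who is counted and how an SAE is defined are in the text and need no assumption.

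The consequence is less certain. Post-treatment events may be undercounted, and serious events below grade 4 judged unrelated may be missing from the SAE proportion. The documents give no event, early-stop or loss rates, so the size of any undercount is unknown. A reader might infer that the comparison between arms is biased towards the product, but the documents do not show this.

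**What to change.** 1. In section 6.4, state that safety is a secondary objective, as in Table 1.
2. Define the safety set as all patients who received at least one dose, by treatment received, including early stoppers and culture-negative patients. Align 4.3 and 4.4.6.1 with it.
3. Report AE and SAE proportions by arm for 0-72 h and through the 28-day follow-up. State when the 28 days begin, and add the follow-up contacts to Appendix I.
4. In section 4.12, replace the exclusion of lost patients by counting their events up to last contact.
5. Reconcile 4.11 with 4.3, 4.9 and 4.12 so that the weekly calls cover every dosed patient who has not withdrawn consent.
6. In Appendix II, open the SAE definition with any untoward medical occurrence in place of an adverse reaction, to match 4.7.1.

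The cost is wording, one more safety table and up to four calls (28/7) for each early stopper. The sample size does not change.
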